### 3 OBJECTIVES

#### 3.1 Primary endpoint

The number of subjects that achieve a 50 percent or greater reduction in their PASI with intervention as compared to placebo.

#### 3.2 Secondary endpoints

- The number of subjects that achieve a PASI 75, 90, 100 response with intervention as compared to placebo.
- The number of subjects that achieve a PGA score of 0/1 with intervention as compared to placebo.
- The number of subjects that report a pruritus score of 0/1 with intervention as compared to placebo.
- The number of subjects treated that report a DLQI score of 0/1 with intervention as compared to placebo.
- The difference in serum plasma levels of riboflavin and FAD in subjects treated with intervention as compared to placebo.

[figure not shown]

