## 1 SYNOPSIS

The purpose of this investigation is to determine the anti-inflammatory effect of high-dose riboflavin supplementation on chronic plaque psoriasis. Up to fifty volunteers with chronic plaque psoriasis will be recruited for a double-blind, placebo-controlled 28 week prospective study with cross-over of both the intervention and control groups at the 12 week time mark. There will be a 4 week washout period when subjects crossover. Riboflavin will be dosed 400 mg by mouth daily versus placebo. Throughout the study we will perform both clinical and laboratory assessments to measure response. Clinical assessment will include the Psoriasis-Area-and-Severity-Index (PASI), Physician Global Assessment (PGA), Dermatology -Life-Quality-Index (DLQI) and pruritus assessment will be performed at all clinical evaluations. Photographs of volunteers' skin will be taken. Skin punch biopsies of psoriasis plaques and uninvolved skin will be performed at pre-determined time points throughout the study to measure metabolomics and RNA profiling as well as histologic markers. Patients will also have regular blood draws to follow plasma measurements of riboflavin and Flavin-adenine-dinucleotide (FAD).

The primary objective is to demonstrate the superiority of riboflavin as compared to placebo at achieving a PASI 50 response (a 50% or greater improvement in PASI from baseline). Secondary objectives include, measuring the efficacy of the intervention at achieving a PGA, DLQI, or pruritus assessment score of 0/1. All statistics will be performed on a modified intent-to-treat population.

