## **6.2 Admission/Day 0**

1. Measure vital signs.
2. Review medical history, adverse events and concomitant medications.
3. Skin Exam: Complete PASI, PGA, DLQI, and pruritus assessment using visual analog scale (VAS).
4. Photographs will be taken of significant lesions.
5. Randomize patient
6. For females of childbearing potential, obtain a negative urine pregnancy test.
7. 20 mL of blood will be drawn for measuring plasma levels of riboflavin and FAD.
8. Two psoriatic normal (PN) and two psoriatic plaque (PP) skin samples will be obtained (four total at this visit). These will be performed under local anesthesia (1% lidocaine with epinephrine) using a 6 mm skin punch to obtain skin through to subcutaneous fat. Closures will be made with 4-0 prolene sutures that should be removed in two weeks. Verbal wound care instructions will be provided.
9. Dispense medication.

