## **6.3 Return Visits - Weeks 2, 6, 12, 16, 18, 22 and 28**

1. Measure vital signs.
2. Review medical history, adverse events and concomitant medications.
3. Skin Exam: Complete PASI, PGA, DLQI, and pruritus assessment using visual analog scale (VAS).
4. For females of childbearing potential, obtain a negative urine pregnancy test.
5. Photographs will be taken of significant lesions on weeks 0, 12, 16, and 28.

**Title:** The Effect of Riboflavin on Moderate to Severe Plaque Type Psoriasis

**Principal Investigator:** [name]

6. One PP and one PN 6 mm punch biopsy will be performed at week 12. These will be performed as described above. This will be a total of 6 biopsies throughout the study.
7. 20 mL of blood will be drawn for measuring plasma levels of riboflavin and FAD on weeks 2, 12, 18 and 28.
8. 9 mL of blood will be drawn for measuring CBC, CMP on weeks 12 and 28.
9. At week 12 all residual medication will be collected and counted in preparation for patients to cross-over. There will be a four week wash-out period between weeks 12 and 16. At week 16 new medication will be provided and the data from this visit will be used as our new baseline for the second part of the study.
10. At week 28, all residual medication will be collected and counted.

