**Table 1. Time and Events Table**

|   | Screening | Week 0 | Week 2 | Week 6 | Week12 | Week 16 | Week 18 | Week 22 | Week 28 | Week 32
(phone) |
|---|-----------|--------|--------|--------|--------|---------|---------|---------|---------|--------------------|
| Obtain informed Consent                 | X         |        |        |        |        |         |         |         |         |                    |
| Randomization                           |           | X      |        |        |        |         |         |         |         |                    |
| Medical and Psoriatic Treatment History | X         | X      | X      | X      | X      | X       | X       | X       | X       | X                  |
| Physical Exam                           | X         |        |        |        |        |         |         |         |         |                    |
| Con Meds/AE                             | X         | X      | X      | X      | X      | X       | X       | X       | X       | X                  |
| Vital Signs                             |           | X      | X      | X      | X      | X       | X       | X       | X       |                    |
| PASI, PGA                               |           | X      | X      | X      | X      | X       | X       | X       | X       |                    |
| DLQI/ Pruritus VAS                      |           | X      | X      | X      | X      | X       | X       | X       | X       |                    |
| Urine Pregnancy Test for WOCBP          | X         | X      | X      | X      | X      | X       | X       | X       | X       |                    |
| Blood Draw (CBC/CMP)                    | X         |        |        |        | X      |         |         |         | X       |                    |
| Blood Draw (FAD and Riboflavin)         |           | X      | X      |        | X      |         | X       |         | X       |                    |
| Biopsies                                |           | X      |        |        | X      |         |         |         |         |                    |
| Photographs                             |           | X      |        |        | X      | X       |         |         | X       |                    |
| Collect Residual Medication             |           |        |        |        | X      |         |         |         | X       |                    |

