## 16 Appendix D - Pruritus Assessment

### Pruritus Assessment

Please rate your itch over the last 24 hours from 1-10 (10 being the worst)?

The figure shows a visual analog scale titled "ITCH RATING SCALE". It is enclosed in a rectangular border. At the top, the title "ITCH RATING SCALE" is centered in a light gray box. Below the title, the instruction "Draw a single, vertical line on the scale below to indicate how bad you feel your itching is today:" is written. Underneath the instruction is a horizontal line with 10 vertical tick marks, representing a scale from 1 to 10. The left end of the scale is labeled "NO ITCHING" and the right end is labeled "FREQUENTLY INTERFERES WITH DAILY ACTIVITIES".

**Figure 1.** Visual analog scale

**Title:** The Effect of Riboflavin on Moderate to Severe Plaque Type Psoriasis  
**Principal Investigator:** [name]

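### The pruritus endpoint counts scores of 0 or 1, but the Appendix D form runs from 1 to 10 and no rule turns a drawn mark into a score

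*Combined protocol and SAP*

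**What the plan says.** Section 3.2 (Secondary endpoints) defines pruritus response as "The number of subjects that report a pruritus score of 0/1 with intervention as compared to placebo". The Synopsis uses the same threshold, describing the secondary objectives as "measuring the efficacy of the intervention at achieving a PGA, DLQI, or pruritus assessment score of 0/1".

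Appendix D is the only pruritus form, and it carries two items. The first is a numeric question: "Please rate your itch over the last 24 hours from 1-10 (10 being the worst". The second is a line with the instruction "Draw a single, vertical line on the scale below to indicate how bad you feel your itching is today". The appendix text describes that line as having 10 tick marks and standing for a 1 to 10 scale. The no-itching label is at the left end, and the label at the right end refers to frequent interference with daily activities.

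The visit procedures name the instrument. Section 6.2 has "Skin Exam: Complete PASI, PGA, DLQI, and pruritus assessment using visual analog scale (VAS", Section 6.3 repeats "pruritus assessment using visual analog scale (VAS", and Table 1 lists "DLQI/ Pruritus VAS". Section 11 mentions dichotomized improvement for key clinical endpoints and a Wilcoxon test for ordinal or nominal assessments. It gives no rule for measuring, rounding or dichotomizing a pruritus mark.

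**The concern.** A responder threshold has to be expressed on the scale that the form records. Here it includes a value that the form does not offer. A 0/1 threshold suggests none or minimal itch, in parallel with the PGA endpoint. On a 1 to 10 scale it means the bottom score only, and one step above the minimum is a 2, which fails.

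In addition, a drawn mark is not a number until someone reads it. With no reading rule, the same mark close to the left end can be a responder or a non-responder. That choice would be made outside the plan, possibly after results are known, and two analysts could report different counts from the same forms.

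**Working it through.** The plan states no figure to reproduce. The check sets the texts side by side and then works out how much the missing reading rule matters.

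**Step 1: threshold against instrument.**

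| Source | Content |
|---|---|
| Synopsis; Section 3.2 | responder = score of 0 or 1 |
| Appendix D, question | 1 to 10, 10 worst |
| Appendix D, line | 10 tick marks, described as 1 to 10, no itching at the left end |
| Appendix B (PGA, for comparison) | 0 = clear and 1 = minimal, both printed and defined |

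Of the whole numbers 1 to 10, only 1 belongs to the set {0, 1}. The PGA endpoint uses the same 0/1 threshold, and its form supports it. The pruritus form does not.

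**Step 2: which item supplies the score.** Sections 6.2 and 6.3 and Table 1 all name the VAS, so the line is the natural source. The numeric question is nevertheless printed on the same form, with a different recall period (the last 24 hours, against today on the line).

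**Step 3: from mark to score.** Let f be the position of the mark as a fraction of the line from the left end, L the value of the left end and H the value of the right end. On a linear scale:

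score = L + (H − L) × f

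The responder zone is bounded by

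f = (c − L) / (H − L)

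with c = 1 if the mark is measured exactly (score ≤ 1), or c = 1.5 if it is rounded to the nearest whole number with halves rounded up (score < 1.5).

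*The line as Appendix D describes it (L = 1, H = 10):*
- exact: (1 − 1)/9 = 0, so only a mark on the left end point itself qualifies;
- rounded: (1.5 − 1)/9 = 0.056, so marks within less than the first 5.6% of the line qualify.

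*If a 0-10 line was intended (an assumption; no section describes one):*
- exact: (1 − 0)/10 = 10%;
- rounded: (1.5 − 0)/10 = 15%.

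*If the ten ticks were coded 0 to 9 (also an assumption):*
- exact: (1 − 0)/9 = 11.1%;
- rounded: (1.5 − 0)/9 = 16.7%.

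**Step 4: reading the result.** On the form as described, the two readings disagree for marks beyond the left end point and short of 5.6% of the line. A mark on the left end point is a responder under either, and a mark at 5.6% or beyond is a responder under neither. The wider zones arise only if the line is given a coding that the documents do not state. All of these are shares of the line, not of subjects. The documents give no itch distribution, so the number of subjects affected cannot be worked out.

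**The case against.** The strongest reply is that the form settles most of this. The line is described as 1 to 10 with no itching at the left, so the left end is 1. The VAS is named three times as the instrument. For the numeric question, an answer of 1 qualifies and an answer of 2 does not. On this view 0/1 is a label carried over from the PGA and DLQI endpoints and simply means the lowest score.

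Much of that stands. A reader might infer that the left end has no value at all, or that the responder zone is open anywhere up to 15% of the line. The documents do not support either reading. The natural value of the left end is 1, and the 10% and 15% zones need a 0-10 line that no section describes. For the same reason, a mark at the position of a 2 on the 1-10 line is a non-responder under both exact and rounded reading. A reader might also infer that nothing identifies which item supplies the score; the visit procedures and Table 1 point to the VAS. The two recall periods overlap heavily, and no effect on responder status follows from them alone.

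The reply does not remove the core. If the left end is 1, a score of 0 is impossible on both items, which confirms the mismatch. It also leaves a drawn mark without a measuring or rounding rule. The description in Appendix D is a description of a figure, so any numerals on the printed form should be checked. They could settle the value of the left end, but not how a mark is read.

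**Conclusion.** The point holds as a contradiction between a threshold and its own instrument, together with a missing scoring rule. On the form as described, 0 cannot be recorded and 0/1 reduces to the lowest score. Whether that means the left end point only or the first 5.6% of the line depends on an unstated choice between exact and rounded reading. This rests on a linear scale with the left end equal to 1. The 10% and 15% figures apply only if a 0-10 line was intended.

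A reader might go further and infer that the endpoint cannot be analyzed, or that the treatment comparison is biased. Neither follows. Subjects who mark the left end, or well away from it, are classified the same way under either reading, and the same form serves both treatments. The effect is confined to one secondary endpoint. The PASI 50 primary endpoint and the sample size are untouched. It should be corrected because the responder count cannot be reproduced from the plan as written and the correction is cheap.

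**What to change.** Make the form and the threshold agree in one of two ways:

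- print an explicit 0-10 range on Appendix D, with 0 as no itching, and keep 0/1; or
- keep 1-10 and restate the responder cut-off on that scale in the Synopsis and Section 3.2.

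In either case, state that the VAS mark supplies the score, say how it is measured and whether and how it is rounded, and use a single recall period on the form.

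If data already exist on the current form, record the value of the left end, the reading rule and the matching cut-off before unblinding. Apply them identically in both crossover periods, so that each subject's two periods are scored on the same basis.

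The cost is a corrected form or a revised endpoint line, plus a sentence or two on scoring. Visits, sample size, planned tests and analysis population do not change.

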### 4 STUDY DESIGN

A 28-week, double-blind, placebo-controlled, prospective study with cross-over of both the riboflavin and placebo groups at the 12-week time mark.

Patients will take either 400 mg of riboflavin (“B2-400”) or a placebo by mouth once a day for 12 weeks. There will be a four week wash-out period at week 12 as the groups cross-over.

We propose using a 400 mg daily dose in this clinical trial as there is the most evidence in previous human studies for a clinical effect with this dose. While data suggesting equivalent activity of riboflavin at a lower dose is intriguing, we feel it is premature to choose a lower dose based off the findings in one trial that was stopped prematurely.

Up to 50 subjects will be enrolled. Six skin biopsies will be performed to measure metabolomics profiles, and there will be five blood draws to measure serologic markers.

**Title:** The Effect of Riboflavin on Moderate to Severe Plaque Type Psoriasis  
**Principal Investigator:** [name]

## **5 INVESTIGATIVE PRODUCTS**

### **5.1 B2-400**

B2-400 is a clear gelatin two-piece capsule, size 00, filled with yellow-orange powder equaling 400 mg of Riboflavin (Vitamin B2). The near-infrared spectra of the powder matches the reference standard for riboflavin. The only inactive ingredient is the gelatin in the capsule which is kosher and halal certified. It will be manufactured by Biotech Pharmacal, Inc., Fayetteville, AR. The capsule is to be swallowed whole with food. Product testing shows it meets USP specifications for weight, heavy metals and Prop 65 specifications for heavy metals.

### **5.2 Placebo**

Placebo will consist of a clear gelatin two-piece capsule, size 2, filled with white powder. There will be no active ingredients. Inactive ingredients include the gelatin capsule, which is kosher and halal certified, as well as microcrystalline cellulose powder. It will be manufactured by Biotech Pharmacal, Inc., Fayetteville, AR. The capsule is to be swallowed whole with food. Product testing shows it meets USP specifications for weight, heavy metals and Prop 65 specifications for heavy metals.

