## **9 DRUG ACCOUNTABILITY**

Study administrators, [name] and [name], will communicate with UMHS Pharmacy and coordinate the delivery of investigational medications. All investigational medications will be stored and dispensed to study administrators by the UMHS Research Pharmacy (UH B2D301), per protocol. These administrators will then hand subjects the investigational medication. At weeks 12 and 28, the study administrators will receive any excess investigational medication and record the number of returned capsules in the subjects file.

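### The active and placebo capsules are visibly different and no masking is described, which contradicts the double-blind design

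*Combined protocol and SAP*

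**What the plan says.** **Blinding.** Section 1 (Synopsis) describes a "double-blind, placebo-controlled 28 week prospective study with cross-over of both the intervention and control groups at the 12 week time mark". Section 4 repeats the claim: "A 28-week, double-blind, placebo-controlled, prospective study with cross-over of both the riboflavin and placebo groups at the 12-week time mark".

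**Products.** Section 5.1: "B2-400 is a clear gelatin two-piece capsule, size 00, filled with yellow-orange powder equaling 400 mg of Riboflavin (Vitamin B2"). Section 5.2: "Placebo will consist of a clear gelatin two-piece capsule, size 2, filled with white powder". The inactive ingredients listed for the placebo are the gelatin shell and microcrystalline cellulose. No colour-matching agent is named.

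**Handling.** Section 5.3 sends all product through the research pharmacy but describes no masking step. In Section 9 the pharmacy dispenses to study administrators: "These administrators will then hand subjects the investigational medication". The same staff take back what is left over when each treatment period ends (weeks 12 and 28): "the study administrators will receive any excess investigational medication and record the number of returned capsules in the subjects file". Section 6.3 adds: "At week 12 all residual medication will be collected and counted in preparation for patients to cross-over". The second product is given out at week 16.

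**Assessment.** The item for every return visit in Section 6.3 is "Skin Exam: Complete PASI, PGA, DLQI, and pruritus assessment using visual analog scale (VAS"). Table 1 therefore places the end-of-period PASI and PGA at weeks 12 and 28, the same visits as the capsule counts. Appendices A and B have spaces for the assessor's initials, but no section says who the assessor is or whether that person is separate from those who handle capsules.

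**The concern.** A clear shell shows the colour of its contents, and sizes 00 and 2 are different sizes. As described, the products differ in two visible ways.

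Three groups are affected to different degrees:

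- **Subjects** take a capsule every day. Those who reach week 16 receive the other product and can compare it with what they remember.
- **Study administrators** handle both products, and Sections 5.1 and 5.2 tell anyone holding the protocol which appearance is active.
- **Graders of PASI and PGA** may or may not see capsules. The documents neither say that they do nor prevent it.

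The primary endpoint, PASI 50, is built from graded erythema, thickness, scaling and area. The PGA is a physician's grading, and DLQI and pruritus are reported by the subject. Any of these can move with the expectation of the person scoring. Plasma riboflavin and FAD and the tissue laboratory measures are much less exposed. If blinding fails, a positive PASI 50 result is harder to attribute to riboflavin, and no analysis can recover a lost blind.

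**Working it through.** **Step 1: compare the texts.** This settles the point and needs no arithmetic.

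| Feature | Active (5.1) | Placebo (5.2) | Same? |
|---|---|---|---|
| Shell | clear | clear | yes, so the fill is visible |
| Capsule size | 00 | 2 | no |
| Fill colour | yellow-orange | white | no |

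**Step 2: look for anything that cures it.** Sections 5.3, 6.2, 6.3, 9, 10 and 11, Table 1 and the appendices contain no opaque shell, over-encapsulation, opaque packaging, blinded assessor kept apart from product handling, or check of the blind. The conflict with Sections 1 and 4 is therefore unresolved.

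**Step 3: illustrate the consequence.** The plan gives no figure to reproduce here. Taken from Section 11: two-sided alpha 0.05 and 22 subjects per sequence (2 × 22 = 44). Assumed, with no source in the documents: a PASI 50 rate p0 of 10% or 20% on placebo, no drug effect, and an expectation shift s of 0 to 20 percentage points on riboflavin, so p1 = p0 + s.

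*Within-subject comparison* (exact McNemar test on 44 independent pairs). With within-subject correlation ρ:

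- p11 = p0·p1 + ρ·√[p0(1−p0)·p1(1−p1)]
- p10 = p1 − p11 (response on riboflavin only)
- p01 = p0 − p11 (response on placebo only)

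The number of discordant pairs is binomial(44, p10 + p01). Given that number, the responses favouring riboflavin are binomial with probability p10/(p10 + p01). The rejection probability is summed over both.

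Example with p0 = 0.10, s = 0.10, ρ = 0: p11 = 0.10 × 0.20 = 0.02, p10 = 0.20 − 0.02 = 0.18, p01 = 0.10 − 0.02 = 0.08. The discordant probability is 0.26 and the share favouring riboflavin is 0.18/0.26 = 0.69. The rejection probability is 16.6%.

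*Week-12 comparison of 22 against 22.* All outcomes are enumerated with rates p0 + s and p0, using Fisher's exact test and the uncorrected chi-square test. (Section 11 names McNemar for this between-sequence comparison. The two-group tests are used here because the two groups are different people.)

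Chance of a significant result (%), McNemar at ρ = 0:

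| Base rate | Test | s = 0 | 5 | 10 | 15 | 20 |
|---|---|---|---|---|---|---|
| 10% | McNemar | 1.8 | 5.6 | 16.6 | 34.7 | 56.0 |
| 10% | Fisher | 1.4 | 3.4 | 8.5 | 16.7 | 27.7 |
| 10% | Chi-square | 4.3 | 7.7 | 15.2 | 26.2 | 39.3 |
| 20% | McNemar | 2.7 | 5.3 | 13.2 | 26.7 | 44.3 |
| 20% | Fisher | 2.4 | 3.5 | 6.8 | 12.5 | 20.6 |
| 20% | Chi-square | 5.1 | 6.9 | 11.8 | 19.6 | 29.8 |

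Sensitivity of McNemar at a 10% base rate and a 10-point shift: ρ = 0.3 gives 20.9% and ρ = 0.5 gives 24.7%. With 36 pairs instead of 44 (ρ = 0) the result is 12.7%. At s = 0 and ρ = 0.5 with 44 pairs it is 0.5%, the lowest blinded value quoted.

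**The case against.** The contradiction itself is hard to dispute. Its reach can be questioned on five grounds.

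1. **Assessor exposure is not shown.** PASI is scored by an assessor, while Section 9 gives capsule handling to designated study administrators, and Appendices A and B have their own assessor initials. The grader may never see a capsule. This stands as an unknown. It is not a safeguard, because no section says the two roles are held by different people.
2. **Subjects have seen only one product before week 16.** Residual medication is collected at week 12, so any comparison is made from memory after four weeks. The documents as supplied do not show whether subjects are told what each product looks like. This stands: subject unblinding is weaker in the first period, including for the week-12 comparison. It does not help the second period or the pooled analysis, and differences in size and colour are easy to remember.
3. **Masking may be set out elsewhere**, for example in a pharmacy manual. That is possible, but Sections 5.1 and 5.2 would still need correcting, because they describe products that do not match.
4. **The illustration proves little.** Any assumed shift in favour of riboflavin must raise the rejection rate, and blinded values below 5% largely reflect the conservatism of exact tests. This is correct. The figures show what a shift would do, not that one will occur.
5. **The cost of new capsules is undocumented.** This is also correct.

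None of these reconciles the product descriptions with a double-blind design.

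**Conclusion.** The concern holds and must be fixed before product is dispensed. On the protocol's own descriptions the two products can be distinguished by sight, and nothing in the supplied text masks them. Blinding of subjects and study administrators cannot be relied on, with subjects most exposed from week 16. Blinding of the PASI and PGA assessor is unprotected, and whether it would actually be lost is not documented.

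Confidence in the contradiction is high, and it rests on no calculation. The size of any bias is not established. Under the assumed settings a 10-point expectation shift gives a 6.8% to 24.7% chance of a significant result with no drug effect, against 0.5% to 5.1% when blinded. Those ranges depend on assumed base rates, shifts and correlations, and on the shift acting on the PASI score.

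**What to change.** 1. **Match the products.** Amend Sections 5.1 and 5.2 so that both are supplied in identical opaque capsules of the same size, with inert filler as needed and the riboflavin content unchanged. Size 00 already holds the active fill, and the placebo already uses microcrystalline cellulose.
2. **Separate the roles.** State in Sections 6.2, 6.3 and 9 that those who grade PASI and PGA do not hand out, receive or count capsules.
3. **Optionally, measure the blind.** Record the subject's and the assessor's guess of allocation at weeks 12 and 28. This measures the blind and does not repair it.
4. **If masking already exists**, describe it in Sections 5.1 to 5.3.
5. **If matching cannot be done**, remove the double-blind claim from the Synopsis and Section 4, state who does remain blinded (for example, graders kept away from capsules), and report the unblinding as a limitation.

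**Cost.** One manufacturer is named for both products, so the change there is an opaque shell for both and a larger placebo capsule. This should be modest if made before dispensing, but the documents give no price or lead time. Keeping graders away from capsules means dividing tasks at weeks 0, 12, 16 and 28. The rest is protocol wording. No additional patients or study procedures are needed.
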